1.3 Risk/Benefit

1.3.1 Potential Risks

Based on preclinical experience and available clinical data from the ongoing Phase 1/2a CICILIA study, there are no specific adverse reactions to be inferred as "expected" at the 20 mg every 2 weeks (Q2W) dose level of CyPep-1.

1.3.2 Benefit

The efficacy and safety data, together with the pharmacodynamic data obtained from this study, will help design subsequent clinical studies in the target populations. Treatment of patients with CyPep-1 in combination with pembrolizumab is expected to result in improvement or stabilization of the disease state of the patients.

1.4 Coronavirus Disease 2019 Impacts

In March 2020, the Coronavirus Disease 2019 (COVID-19), caused by infection with severe acute respiratory syndrome coronavirus 2 (SARS-CoV-2), was characterized as a pandemic by the World Health Organization. The COVID-19 pandemic has impacted clinical studies worldwide due to quarantines, study site closures, travel limitations, diversion of resources, and/or general interruptions in study-related procedures.

The impacts of the COVID-19 pandemic on the outcomes of this study, including any protocol deviations that result from COVID-19 illness and/or COVID-19 control measures, will be discussed in the Clinical Study Report (CSR).

2 STUDY OBJECTIVES AND ENDPOINTS

The study objectives and endpoints are provided in Table 6.

Table 6. Objectives and Endpoints

Primary Objectives	Primary Endpoints			
Phase 1b				
Confirm the recommended CyPep-1 dose (20 mg Q2W) when administered by IT injection in combination with pembrolizumab	 Incidence, frequency, and seriousness of TEAEs; Incidence of DLTs; and Changes from baseline in vital signs, body weight, 12-lead ECG parameters, and laboratory assessments. 			
Phase 2a				
Assess the anti-tumor activity of CyPep-1 administered by IT injection in combination with pembrolizumab	RECIST v1.1			
Secondary Objectives	Secondary Endpoints			
Evaluate the PK of CyPep-1 in combination with pembrolizumab Phase 2a	 Plasma concentration-time profile of CyPep-1 and, if detectable, the following derived PK parameters: AUC; C_{max}; T_{max}; CL; t½; and VD. 			
Expand evaluation of efficacy CyPep-1 + pembrolizumab Evaluate the safety and tolerability of CyPep-1 in combination with pembrolizumab	 ORR according to iRECIST; DCR according to iRECIST and RECIST v1.1; DoR according to iRECIST and RECIST v1.1; PFS according to iRECIST and RECIST v1.1; and OS for up to 26 months from Cycle 1 Visit 1. Incidence, frequency, and seriousness of TEAEs; and Changes from baseline in vital signs, body weight, 12-lead ECG parameters, and laboratory assessments. 			

Table 6. Objectives and Endpoints (Continued)

Exploratory Objectives	Exploratory Endpoints
Analyze changes in biomarkers and tumor kinetics	 Number and relative change of tumor infiltrating immune cells; Expression of selected immune cell biomarkers; Change from baseline in target tumor lesion size over time, overall, and by injected versus non-injected lesions; Maximum decrease from baseline in target tumor lesions, overall, and by injected versus
associated with the mode of action of CyPep-1 and	non-injected lesions; and
pembrolizumab by tumor biopsy from injected lesions	• Changes in new lesions treated with CyPep-1.
Expand evaluation of anti-tumor activity of CyPep-1	ORR according to itRECIST
and pembrolizumab	

AUC = area under the curve; CL = systemic clearance; C_{max} = peak plasma concentration; DCR = Disease Control Rate; DLT = dose-limiting toxicity; DoR = Duration of Response; ECG = electrocardiogram; iRECIST = immune-Response Evaluation Criteria in Solid Tumors; IT = intra-tumoral; itRECIST = intra-tumoral-Response Evaluation Criteria in Solid Tumors; ORR = Objective Response Rate; OS = Overall Survival; PFS = Progression Free Survival; PK = pharmacokinetic(s); Q2W = every 2 weeks; Q6W = every 6 weeks; RECIST = Response Evaluation Criteria in Solid Tumors; $t_{1/2}$ = elimination half-life; TEAE = treatment-emergent adverse event; $t_{1/2}$ = time to reach peak plasma concentration; $t_{1/2}$ = volume of distribution.

3 STUDY DESCRIPTION

3.1 Summary of Study Design

This is an open-label, multi-center, non-randomized Phase 1b/2a study. The Phase 1b portion of the study (ie, the first 6 patients enrolled) will confirm the recommended CyPep-1 dose of 20 mg Q2W in combination with pembrolizumab 400 mg Q6W (see Section 3.1.1). The patients from the Phase 1b portion will continue to the Phase 2a portion of the study (approximately 90 patients in total will be enrolled, with 30 patients per arm). The Phase 2a portion of the study will have 3 arms including patients with advanced or metastatic head and neck squamous cell carcinoma (HNSCC), melanoma, or triple-negative breast cancer (TNBC) and will assess the efficacy, safety, and pharmacodynamics of CyPep-1 (20 mg Q2W) when administered directly into measurable tumor lesions in combination with the anti-PD-1 antibody pembrolizumab (400 mg Q6W) (see Section 3.1.2).

[figure not shown]
The following 3 study arms will be included in the study:

- Arm A will include patients who meet the following criteria:
 - Have histologically confirmed diagnosis of HNSCC (including nasopharyngeal squamous cell carcinoma);
 - o Have advanced or metastatic HNSCC incurable by standard of care therapies; and
 - Have recurrent or metastatic HNSCC that has progressed on or failed both platinum-based chemotherapy AND an ICI (given either sequentially or concurrently).
 - Note: Patients who received platinum-based chemotherapy with concurrent radiation for locally advanced HNSCC and experienced disease progression within 6 months may also be considered as having disease progression on platinum-based chemotherapy.
- Arm B will include patients who meet the following criteria:
 - o Have histologically confirmed diagnosis of malignant melanoma;
 - O Do not have uveal melanoma;
 - o Have advanced or metastatic melanoma incurable by standard of care therapies;
 - o Have received a combination of a BRAF inhibitor and a MEK inhibitor if diagnosed with a BRAF-mutated melanoma and if clinically indicated; and
 - Have failed or progressed on or after treatment with a checkpoint inhibitor administered either as monotherapy or in combination with other checkpoint inhibitors or other therapies.
- Arm C will include patients who meet the following criteria:
 - o Have histologically confirmed diagnosis of TNBC as per American Society of Clinical Oncology/College of American Pathologists (ASCO/CAP) guidelines;²⁴
 - o Have advanced or metastatic TNBC incurable by standard of care therapies;

- Have received sacituzumab govitecan chemotherapeutic treatment if clinically indicated;
 and
- Have failed or progressed on or after treatment with a checkpoint inhibitor administered either as monotherapy or in combination with other therapies (if ICI eligible based on PD-L1 status) OR have received prior systemic therapy with either an anthracycline- or taxane-containing regimen (if ICI non-eligible based on PD-L1 status).

The study enrollment will follow a 1-stage design as shown in Figure 2.

Figure 2. One-Stage Study Design

HNSCC = head and neck squamous cell carcinoma; N = number of patients planned for each arm; TNBC = triple-negative breast cancer.

After signing the informed consent form (ICF), patients will be assessed for study eligibility. The Screening Visits will be completed within 28 days of the start of treatment. Screening will include the identification of measurable tumor lesions as per Response Evaluation Criteria in Solid Tumors (RECIST) version (v)1.1. Patients with lesions appropriate for IT injection with CyPep-1 (injected lesions) should be identified and will receive up to 4 mL of CyPep-1, after it is ensured that they meet the Inclusion Criteria (see Section 4.1) and none of the Exclusion Criteria (see Section 4.2) per the Investigator.

[figure not shown]
When more than 1 measurable lesion is present at screening, up to a maximum of 5 lesions total (and a maximum of 2 lesions per organ) representative of all involved organs should be identified as target lesions. Both injected and non-injected lesions identified at screening per RECIST v1.1 may be target lesions and will be recorded and measured at baseline and followed for response. If a patient only has 1 measurable lesion, then this lesion will be identified as an injected lesion and will be evaluated for efficacy as a target lesion. In these cases, IT therapy will not be considered a loco-regional therapy exclusionary for measurability, and single lesions may be designated as injectable target lesions per intratumoral-RECIST (itRECIST).

After each of the first 3 CyPep-1 injections, a telephone call will be conducted once daily for the first 2 days and once approximately 1 week post injection to assess patients' symptoms and temperatures.

AEs will be recorded from the time of signing the ICF until 30 days after the last dose of study treatment. All AEs that are considered serious will be monitored and recorded until 90 days (30 days if patients initiate new anti-cancer therapy) after the last dose of study treatment. Other safety assessments will be conducted as described in the Schedule of Assessments (Appendix A). The Data Monitoring Committee (DMC) will review accumulating safety data in regular intervals as per the DMC charter.

An overview of the study flow is presented in Figure 3.

Figure 3. Study Flow

The Phase 1b portion of the study will comprise of the first 6 patients enrolled in the study. After the first 6 patients have completed the DLT period (Cycle 1 [initial 6 weeks of study treatment]), the DMC and Sponsor will review safety and tolerability data prior to the enrollment of the remainder of the patients into the Phase 2a portion of the study.

DLT = dose-limiting toxicity; DMC = Data Monitoring Committee; EoT = End of Treatment; FU = follow-up; IT = intra-tumoral(ly); IV = intravenous(ly); n = number of treatment cycle; Q6W = every 6 weeks; Q8W = every 8 weeks; Screen = screening.

3.1.1 Phase 1b

The Phase 1b portion of the study will comprise of the first 6 patients enrolled in the study to confirm the recommended CyPep-1 dose (20 mg Q2W) based on safety and tolerability observations.

Patients will receive IT injections of a fixed concentration of CyPep-1 Q2W beginning at Cycle 1 Visit 1. Pembrolizumab will be administered IV at a fixed dose Q6W beginning at Cycle 1 Visit 1. Patients must be observed for 4 hours post injection for PK monitoring on Cycle 1 Day 15. The plasma concentration-time profile of CyPep-1 and, if detectable, the derived PK parameters will be assessed.

The DLT period for the Phase 1b portion of the study will be Cycle 1 (initial 6 weeks of study treatment); see Section 3.1.1.1. After the first 6 patients have completed the DLT period, the DMC and Sponsor will review safety and tolerability data prior to the enrollment of the patients into the Phase 2a portion of the study. If \leq 2 DLTs are observed in the first 6 patients, then the recommended CyPep-1 dose will be confirmed and enrollment of the remainder of the patients should continue.

If >2 of the 6 patients develop a DLT at the recommended CyPep-1 dose level (5 mg/mL dose concentration), then the MTD of CyPep-1 will be assumed to have been exceeded and dose de-escalation will be conducted to determine the MTD. At least 6 patients will be treated at CyPep-1 dose level -1 (2 mg/mL dose concentration). If necessary, due to >2 DLTs in the dose level -1 cohort, a further reduction to dose level -2 (0.5 mg/mL dose concentration) will be performed.

Dose de-escalation will proceed according to the following rules:

- If 2 out of 6 patients develop a DLT, the MTD will be declared; or
- If >2 out of 6 patients develop a DLT, the dose will be de-escalated to the next lower dose.

The MTD will guide confirmation, by agreement of the DMC and the Sponsor, of a recommended Phase 2 dose (RP2D). The RP2D may be equivalent to the MTD or may be a dose below the MTD and will be dependent on an acceptable tolerability profile and manageable AEs.

The patients from Phase 1b will continue to the Phase 2a portion of the study. After the DMC reviews the safety data, feedback will be provided to the Sponsor regarding the further conduct of the study, see Section 3.1.2.

3.1.1.1 Dose-limiting toxicities

All toxicities will be graded using National Cancer Institute (NCI) Common Terminology Criteria for Adverse Events (CTCAE) v5.0 based on the Investigator assessment.

The DLT window of observation will be during Cycle 1 (initial 6 weeks of study treatment).

The occurrence of any of the following toxicities during Cycle 1 will be considered a DLT, if assessed by the Investigator to be possibly, probably, or definitely related to study treatment administration:

- 1. Grade 4 non-hematologic toxicity (not laboratory);
- 2. Grade 4 hematologic toxicity lasting ≥7 days, except thrombocytopenia:
 - o Grade 4 thrombocytopenia of any duration; or
 - o Grade 3 thrombocytopenia associated with clinically significant bleeding.
- 3. Any non-hematologic AE ≥Grade 3 in severity should be considered a DLT, with the following exceptions:
 - o Grade 3 fatigue lasting ≤3 days;
 - o Grade 3 diarrhea, nausea, or vomiting unless it persists for >3 days despite the use of anti-emetics or anti-diarrheals per standard of care; or
 - o Grade 3 rash without use of corticosteroids or anti-inflammatory agents per standard of care.
- 4. Any Grade 3 or Grade 4 non-hematologic laboratory value if:
 - o Clinically significant medical intervention is required to treat the patient;
 - o The abnormality leads to hospitalization;
 - o The abnormality persists for >1 week; or

- The abnormality results in a drug-induced liver injury.
- Exceptions: Clinically non-significant, treatable, or reversible laboratory abnormalities including liver function tests, uric acid, etc. Isolated laboratory abnormalities ≥Grade 3 (not present at baseline) that resolve to <Grade 1 in <3 days without clinical sequelae or need for therapeutic intervention.

- 5. Febrile neutropenia Grade 3 or Grade 4:
 - o Grade 3 is defined as absolute neutrophil count (ANC) <1000/mm³ with a single temperature of >38.3°C (101°F) or a sustained temperature of ≥38°C (100.4°F) for more than 1 hour; or
 - o Grade 4 is defined as ANC <1000/mm³ with a single temperature of >38.3°C (101°F) or a sustained temperature of ≥38°C (100.4°F) for more than 1 hour with life-threatening consequences and urgent intervention indicated.
- 6. Prolonged delay (>2 weeks) in initiating Cycle 2 due to treatment-related toxicity;
- 7. Delay in administration of CyPep-1 for >7 days;
- 8. Any single instance of aspartate aminotransferase and/or alanine aminotransferase >3 × upper limit of normal (ULN) AND concurrent total bilirubin >2 × ULN that is not thought to be due to disease progression or other medical illness (ie, liver function abnormalities that meet the criteria of Hy's Law);
- 9. Any treatment-related toxicity that causes the patient to discontinue treatment during Cycle 1;
- 10. Missing >25% of study treatment doses as a result of drug-related AE(s) during the first cycle;
- 11. Grade 5 toxicity.

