8.1 Adverse Events

An AE is defined as any untoward medical occurrence in a clinical investigation patient administered a pharmaceutical product, which does not necessarily have a causal relationship with this treatment. An AE can therefore be any unfavorable and/or unintended sign (including an abnormal laboratory finding), symptom, or disease temporally associated with the use of an investigational medicinal product, whether or not related to the investigational medicinal product. All AEs, including observed or volunteered problems, complaints, or symptoms, are to be recorded on the appropriate eCRF.

AEs, which include clinical laboratory test variables, will be monitored and documented from the time of signing the ICF until 30 days after the last dose of study treatment. All AEs that are considered serious, from the time of signing the ICF until 90 days (30 days if patients initiate new anti-cancer therapy) after the last dose of study treatment, will also be monitored and documented. Patients should be instructed to report any AE that they experience to the Investigator, whether or not they think the event is due to study treatment/procedure. Beginning at screening, Investigators should make an assessment for AEs at each visit and record the event on the appropriate AE eCRF.

Wherever possible, a specific disease or syndrome rather than individual associated signs and symptoms should be identified by the Investigator and recorded on the eCRF. However, if an observed or reported sign or symptom is not considered a component of a specific disease or syndrome by the Investigator, it should be recorded as a separate AE on the eCRF. Additionally, the condition that led to a medical or surgical procedure (eg, surgery, endoscopy, tooth extraction, or transfusion) should be recorded as an AE, not the procedure itself.

Any medical condition already present prior to signing of the ICF should be recorded as medical history and not be reported as an AE unless the medical condition or signs or symptoms present at baseline changes in severity, frequency, or seriousness at any time during the study. In this case, it should be reported as an AE.

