Clinically significant abnormal laboratory or other examination (eg, ECG) findings that are detected during the study or are present prior to signing the ICF and significantly worsen during the study should be reported as AEs, as described below. The Investigator will exercise his or her medical and scientific judgment in deciding whether an abnormal laboratory finding or other abnormal assessment is clinically significant. Clinically significant abnormal laboratory values occurring during the clinical study will be followed until repeat tests return to normal, stabilize, or are no longer clinically significant. Abnormal test results that are determined to be an error should

not be reported as an AE. Laboratory abnormalities or other abnormal clinical findings (eg, ECG abnormalities) should be reported as an AE if any of the following are applicable:

- If an intervention is required as a result of the abnormality;
- If action taken with the study drugs is required as a result of the abnormality; or
- Based on the clinical judgment of the Investigator.

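### DLT criterion 4 contradicts itself: its open-ended exception cancels most events that its treatment and one-week conditions count, and criterion 3 can count the same events

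*Protocol*

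**What the plan says.** Section 3.1.1.1 of the protocol lists eleven DLT criteria. Any one of them suffices, provided the investigator judges the event related to study treatment. Four parts matter here.

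- **Criterion 1** is confined to clinical events: "Grade 4 non-hematologic toxicity (not laboratory" (the bracket closes there).
- **Criterion 3** has no such bracket: "Any non-hematologic AE ≥Grade 3 in severity should be considered a DLT, with the following exceptions". The exceptions it lists are for fatigue, diarrhea, nausea or vomiting, and rash.
- **Criterion 4** covers Grade 3/4 non-hematologic laboratory values that meet any of four conditions. Two of these are "Clinically significant medical intervention is required to treat the patient" and "The abnormality persists for >1 week"; the others are hospitalization and drug-induced liver injury.
- **Criterion 4's exceptions** come in two sentences. The first is "Exceptions: Clinically non-significant, treatable, or reversible laboratory abnormalities including liver function tests, uric acid, etc". The second is tightly bounded: isolated abnormalities that fall below Grade 1 in under 3 days, with no sequelae and no therapy.

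Section 8.1 defines an AE to include "any unfavorable and/or unintended sign (including an abnormal laboratory finding". It requires a laboratory abnormality to be reported as an AE in several situations, among them "If an intervention is required as a result of the abnormality".

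The synopsis repeats the DLT wording. SAP 3.7.2 refers back to Section 3.1.1.1, adds no rule of its own, and plans a listing of DLTs.

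**The concern.** The first exception turns on whether an abnormality can be treated or reversed, and sets no limit on how long it lasted or what treatment it took. A value that was treated successfully meets both the intervention condition and the exception. So does a value that lasted ten days and then recovered, through the one-week condition. Nothing says which prevails. Criterion 3 may then count as an AE what criterion 4 has just excused.

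DLT incidence is a Phase 1b primary endpoint (SAP 2.2.1). Under Protocol 3.1.1, two or fewer DLTs in six patients confirm the 20 mg dose and more than two call for de-escalation, subject to review by the DMC and the sponsor. With two clear DLTs, one contested patient would decide the matter.

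**Working it through.** The documents give no figure to reproduce, so the check is one of logic, followed by its possible size.

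**1. The readings side by side.** Take a related Grade 3 ALT rise in Cycle 1 that is treated, resolves in 10 days and has normal bilirubin. Section 8.1 makes it an AE because it needed intervention.

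| Criterion 4 exception | Criterion 3 covers laboratory AEs | Criterion 3 excludes them |
|---|---|---|
| Narrow (yields to the four conditions) | DLT (criteria 3 and 4) | DLT (criterion 4) |
| Broad (overrides them) | DLT (criterion 3) | Not a DLT |

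The event is missed in one cell of four. An untreated event of the same length works out the same way once it is reported as an AE. If no action on study drug is needed, Section 8.1 leaves that to the investigator's judgment.

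**2. What the other criteria catch.** Criterion 8 (Hy's Law) needs raised bilirubin. Criteria 6, 9 and 10 need a delayed Cycle 2, discontinuation or missed doses. Criterion 7 is "Delay in administration of CyPep-1 for >7 days". To test criterion 7, assume an injection on day 0, the next due on day 14, onset on day d = 0 to 13, duration L days, and CyPep-1 held until resolution. Then delay = max(0, d + L − 14), and the event is caught if the delay exceeds 7 days.

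- L = 8: longest delay 13 + 8 − 14 = 7, so caught on 0 of 14 onset days
- L = 10: caught on 2 of 14 (d = 12 and 13; longest delay 9 days, so criterion 6 is not met)
- L = 14: caught on 6 of 14
- L = 21: caught on 13 of 14

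The gap under the one-week condition is therefore mainly events of about one to two weeks. A shorter event is affected only through the intervention condition.

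**3. Effect on the estimate.** Exact (Clopper-Pearson) 95% intervals:

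- 2/6 = 33% (4% to 78%)
- 3/6 = 50% (12% to 88%)

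**4. Evidence on frequency.** The protocol's Table 5 (CICILIA) shows no severe related event in 3 + 5 + 6 = 14 subjects. The exact 95% upper limit is 1 − 0.025^(1/14) = 23%. Those are data on CyPep-1-related events and do not establish the rate for the combination.

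**5. Probability of a changed result.** Let q be the chance that a patient has only a contested event and c the chance of a clear DLT. Both are assumed: q = 2% to 5%, c = 5% to 10%.

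Reported count changes: 1 − (1 − q)^6 = 11.4% at q = 0.02 and 26.5% at q = 0.05.

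Dose decision differs: P(X ≥ 3; 6, c + q) − P(X ≥ 3; 6, c), with X binomial.

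| q | c | Calculation | Result |
|---|---|---|---|
| 0.02 | 0.05 | 0.00584 − 0.00223 | 0.4% |
| 0.02 | 0.10 | 0.02609 − 0.01585 | 1.0% |
| 0.05 | 0.05 | 0.01585 − 0.00223 | 1.4% |
| 0.05 | 0.10 | 0.04734 − 0.01585 | 3.1% (0.03149; at most 3.2% if rounded up) |

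**The case against.** The strongest reply is that the ALT example is a DLT on either natural construction. If the exception is narrow, criterion 4 counts it. If it is broad, it is still only an exception to criterion 4, and criterion 3 read with Section 8.1 counts it. The text also leans towards the narrow reading, since the bounded second exception would add nothing if every reversible abnormality were already excused. This stands, and it limits the point. A reader might infer that any isolated Grade 3/4 laboratory event has no determinable DLT status, but the documents do not support that. Hematologic values, Hy's Law cases, long delays, discontinuations and irreversible untreatable values are settled on any reading. What remains is that the text rules out neither of the two readings which together drop the event.

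A reader might also infer that the planned outputs would hide such events. They would not. SAP 3.7.1 tabulates and lists Grade 3 and higher TEAEs. SAP 3.7.3 gives Grade ≥3 laboratory abnormalities, CTCAE shift tables, ALT/AST multiples of the upper limit and patient listings. None of these, however, shows which events were left out of the DLT count.

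The frequency is probably low. Of the 28 CyPep-1-related events in the protocol's Table 4, the only laboratory term is one Grade 1 platelet decrease, which is hematologic. The DMC and the sponsor also review all the safety data and not merely a tally. Both remarks reduce the consequence; neither repairs the wording.

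**Conclusion.** Wrong as written, minor severity. Criterion 4 states conditions and then an exception that, taken literally, cancels most events the intervention and one-week conditions count. Criterion 3 overlaps it, and nothing in the documents sets precedence. The affected events are related Cycle 1 Grade 3/4 non-hematologic laboratory events that are treated or reversible and are not caught by criteria 6 to 10.

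The size is modest: one patient in six on the reported count, and at most about a 3% chance that the two readings lead to different dose decisions. That figure rests on assumed rates with no source in the documents. The one-to-two-week window rests on an assumed hold to resolution. Table 10, which governs holds for the AEs it lists, is not visible and could lengthen delays; a hold lasting only until a review is completed could shorten them. The DMC charter was not available either.

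It is tempting to say that Phase 2a enrollment hangs on this. SAP Section 1 records that the study was terminated after Phase 1b, so what is left is a primary-endpoint count that can be interpreted and a sound description of the 20 mg dose.

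**What to change.** If the definition is reused, make two short wording changes in Section 3.1.1.1 and the synopsis. State that the criterion 4 exception applies only to abnormalities meeting none of its four conditions. Add to criterion 3 that laboratory events are judged under criterion 4 instead.

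For this trial, mark in the SAP 3.7.2 DLT listing any related Cycle 1 Grade 3/4 non-hematologic laboratory event that was excluded by the exception, and give the DLT count with and without it. If the database is already locked, do this in the CSR.

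The cost is one flag and one extra row for about six patients. The AE, laboratory and concomitant-medication listings already planned (SAP 3.7.1, 3.7.3 and 3.3.7) hold the data.
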